9.2 Procedures for Recording and Reporting Adverse Events

The Medicines for Human Use (Clinical Trials) Regulations 2004 and Amended Regulations 2006 gives the following definitions:

Adverse Event (AE): Any untoward medical occurrence in a subject to whom a medicinal product has been administered including occurrences which are not necessarily caused by or related to that product.

Adverse Reaction (AR): Any untoward and unintended response in a subject to an investigational medicinal product which is related to any dose administered to that subject.

Unexpected Adverse Reaction (UAR): An adverse reaction the nature and severity of which is not consistent with the information about the medicinal product in question set out in the summary of the products characteristics (SmPC).

Serious adverse Event (SAE), Serious Adverse Reaction (SAR) or Unexpected Serious Adverse Reaction (USAR): Any adverse event, adverse reaction or unexpected adverse reaction, respectively, that

Results in death:

Is life-threatening;

Required hospitalization or prolongation of existing hospitalization;

Results in persistent or significant disability or incapacity;

Consists of a congenital anomaly or birth defect.

Fetal death as a result of maternal disease and other events that are primary or secondary outcome measures are not considered to be SAEs and should be reported in the normal way, on the appropriate CRF.

Important Medical Events (IME): Events that may not be immediately life-threatening or result in death or hospitalisation but may jeopardise the patient or may require intervention to prevent one of the other outcomes listed in the definition above should also be considered serious.

Reporting Responsibilities

Rigshospitalet, Denmark has delegated the delivery of the Sponsor's responsibility for Pharmacovigilance (as defined in Regulation 5 of the Medicines for Human Use (Clinical Trials) Regulations 2004 to the GCP unit in Copenhagen.

All SAEs, SARs and SUSARs (excepting those specified in this protocol as not requiring reporting) will be reported immediately (and certainly no later than 24hrs) by the Investigator to the KHP-CTO and CI for review in accordance with the current Pharmacovigilance Policy.

The GCP unit in Copenhagen will report SUSARs to the relevant regulatory authorities (MHRA in the UK, competent authorities of other EEA (European Economic Area) states in which the trial is taking place.

The Chief Investigator will report to the relevant ethics committee. Reporting timelines are as follows:

- SUSARs which are fatal or life-threatening must be reported not later than 7 days after the sponsor is first aware of the reaction. Any additional relevant information must be reported within a further 8 days.
- SUSARs that are not fatal or life-threatening must be reported within 15 days of the sponsor first becoming aware of the reaction.
- The Chief Investigator and GCP unit in Copenhagen (on behalf of the sponsor), will submit a Development Safety Update Report (DSUR) relating to this trial IMP, to the MHRA and REC annually.

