4.1.2 Secondary endpoints

The pre-defined secondary endpoints include:

The pre-defined secondary endpoints include:

- 1. Pregnancy loss < 10 weeks gestation
- 2. Pregnancy loss > 10th week of gestation of a morphologically normal fetus documented by ultrasound or by direct examination of the fetus
- 3. Premature birth of a morphologically normal neonate < 34 weeks due to any of: pre-eclampsia, eclampsia, recognized features of placental insufficiency.
- 4. Gestational age at delivery
- 5. Birth weight
- 6. Delivery by Caesarean section
- 7. Apgar score < 7 at 5 min
- 8. Neonatal morbidity (bleeding or thrombotic complications, infections, congenital abnormalities)
- 9. Days to hospital discharge following delivery (mother & child)
- 10. Thrombotic events in the mother during pregnancy and 6 weeks post-partum.
- 11. Days of neonate in special care
- 12. Safety and tolerability of hydroxychloroquine in the mother and in the neonate

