When reviewing the literature on the use of 200 mg daily, several studies have focused on possible long-term effects of HCQ in children exposed in utero or during lactation (in one study the average daily maternal dose of hydroxychloroquine was 317 mg and in the second study and in the second study the daily dose was 200 mg) [75, 76]. No decrease in visual acuity, visual field or colour vision, changes in electroretinogram and electro-oculogram were detected in a series of six children studied during the first year of life and up to 4 years of age [77]. A case-control study including 133 pregnancies exposed to hydroxychloroquine found no visual, hearing, growth or developmental abnormalities in children followed up for 108 months. Electrocardiograms of exposed children were normal [51, 78].

What is known about the pharmacokinetics of hydroxychloroquine in pregnancy:

Hydroxychloroquine is a diastereoisomer, has basic properties and is given as the sulphate. While being relatively well absorbed orally and with good bioavailability, hydroxychloroquine has a long and variable plasma terminal elimination half-life (approximately 40-60 days). Hydroxychloroquine undergoes renal clearance [79]. HCQ passes across the placenta, with cord blood concentrations nearly identical to those found in maternal blood, suggesting that during pregnancy the level of exposure to HCQ in mother and fetus is similar[80]. A systematic review including a meta-analysis of hydroxychloroquine exposed pregnant patients with autoimmune diseases including five studies did not show any increased risk of congenital malformations in babies born to mothers who were exposed to hydroxychloroquine in pregnancy[53]. These findings are in line with the more recent systematic review of anti-rheumatics in pregnancies published by Flint et al[9, 44]. To the best of our knowledge no studies exist to inform on the plasma levels of patients exposed to hydroxychloroquine during pregnancy.

Length of hydroxychloroquine exposure:

The maximum length of hydroxychloroquine exposure for women participating in the HYPATIA study is 12 months + the individual pregnancy length, i.e. a maximum total length of 21 months hydroxychloroquine exposure.

The main concern associated with hydroxychloroquine exposure is the development of retinopathy[81]. A number of retrospective and prospective studies have attempted to assess the risk of developing HCQ retinopathy and to identify risk factors for toxicity[48, 82]:

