Post delivery	In case of preterm delivery, record actual date and mode of delivery, gestational age, gender, birth weight, Apgar score, neonatal morbidity (neonatal haemorrhage or thrombotic complications, infections, congenital abnormalities) neonatal days in special care, days to discharge from hospital following delivery (mother and child).

POST PARTUM follow up visit		
Post partum visit (up to 6 weeks post partum)		
Mother	None	
Child	 Record actual date and mode of delivery Gestational age Child gender Birth weight Apgar score Neonatal morbidity (bleeding or thrombotic complications, infections, congenital abnormalities, days in special care) Days of admission (mother & child). 	
US growth scans	Selected centres: bloods for additional research Depending on the individual patient one or more US scans have been performed during pregnancy. All available growth scan results will be recorded. Information will be obtained from maternity records.	
Medication	 All medications will be recorded. Compliance check (Kit number to be noted, date of current kit started & ended, number of tablets taken, number of tablets missed) The patient will be asked to bring unused trial medication and empty packaging (number of tablets taken & number of tablets missed will be recorded). 	
Adverse events & Adverse pregnancy events	 Enquiry about adverse events including adverse pregnancy events. In case the patient has had a miscarriage this will be noted in the patient notes and the eCRF (not SAE). 	

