8.2 Procedures for Assessing Efficacy Parameters

The primary outcome of the HYPATIA study will be a composite of pregnancy complications as defined above (see primary and secondary outcomes).

Adverse pregnancy outcomes are defined under 'Glossary and Definition' (Section 2). Each adverse pregnancy outcome will be recorded for each individual case. Fetal growth will be assessed by using standardized ultrasound methods. Pre-eclampsia will be diagnosed according to international criteria (see definition in section 2), information with regards to the baby, i.e. gestational age at delivery, birth weight, mode of delivery, Apgar < 7 at 5 min, neonatal morbidity (bleeding or thrombotic complications, infections, congenital abnormalities), number of days in hospital and thrombotic events in the mother during the puerperium. Patients will be consented to give the trial team access to their child's hospital notes if needed (i.e. in case of admission to paediatric special care units or complications such as intraventricular haemorrhage).

Symptoms suggestive of VTE will be evaluated according to the usual diagnostic methods. Patients who present with symptoms suggestive of stroke, myocardial infarction or arterial thrombosis at other sites, generally present as a clinical emergency and clinical and diagnostic information will be obtained retrospectively from the center at which they have been managed.

Efficacy makers are defined as follows:

Miscarriage: The presence of a miscarriage will be determined due to standard medical practice at each participating unit. Usually this will include a history from the patient and at some centers ultrasound for confirmation.

Fetal death: This will be determined by ultrasound according to standard medical practice.

Intrauterine growth restriction: Serial ultrasound assessments according to standard medical practice and the use of growth percentiles will be used to determine the presence or absence of fetal growth restriction (individualized birth weight according to Gardosi).

Placental abruption: Patient history and ultrasound according to standard medical practice.

Premature birth: Birth between 24+0 and 36+6 weeks gestation.

Pre-eclampsia as defined in international guidelines [4]: Hypertension developing after 20 weeks gestation and the coexistence of one or more of the following new onset conditions:

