9.2.1 Adverse events that do not require reporting

Pregnancy itself is well known to potentially causing nausea and tiredness due to several physiological adjustments of the body especially in the first trimester. Any symptoms thought to be related to the physiological changes in pregnancy do not require reporting.

In patients with aPL we expect pregnancy complications. Therefore, aPL related pregnancy complications, such as miscarriage < 10 weeks gestation, miscarriage > weeks 10, premature birth < 34 weeks due to pre-eclampsia, eclampsia or FGR and stillbirth shall not be reported as SAE. For these events we have designed a special section in the electronic database 'adverse pregnancy outcomes', which shall be completed in this case. Any other adverse events will be reported.

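### Neonatal safety is part of endpoint 12, but section 9.2 does not expressly extend adverse event reporting to the live-born baby, and its outcome exemption cuts across the congenital anomaly criterion

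*Protocol*

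**What the plan says.** - **Endpoint.** Section 4.1.2 lists as secondary endpoint 12 "Safety and tolerability of hydroxychloroquine in the mother and in the neonate". The synopsis and section 8.1.1 repeat it.
- **Definitions.** Section 9.2 reproduces the definitions in the UK clinical trial regulations. An adverse event is "Any untoward medical occurrence in a subject to whom a medicinal product has been administered". An adverse reaction is "Any untoward and unintended response in a subject to an investigational medicinal product which is related to any dose administered to that subject". The serious and unexpected categories build on these two terms. One seriousness criterion is a congenital anomaly or birth defect.
- **Exemption.** Section 9.2 then says that fetal death due to maternal disease, and other events that are primary or secondary outcome measures, are not SAEs and go on the ordinary CRF.
- **Catch-all.** Section 9.2.1 lists aPL-related pregnancy complications that are not SAEs and adds: "Any other adverse events will be reported".
- **Neonatal data items.** The post-partum visit in section 7.1 records "Neonatal morbidity (bleeding or thrombotic complications, infections, congenital abnormalities, days in special care"), together with date and mode of delivery, gestational age, gender, birth weight, Apgar score and days of admission. Section 8.2 gives nearly the same list: "neonatal morbidity (bleeding or thrombotic complications, infections, congenital abnormalities), number of days in hospital". The flowchart in 4.3 matches.
- **Event enquiry.** The post-partum visit has an "Enquiry about adverse events including adverse pregnancy events". It does not name the child.
- **Exposure.** Section 5.3 reports "cord blood concentrations nearly identical to those found in maternal blood" and concludes that maternal and fetal exposure are similar.

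**The concern.** The mother takes the drug until the day of delivery, and the protocol itself regards the fetus as similarly exposed. Neonatal safety is a named endpoint, so the protocol should say which events in the baby are collected and how fast a serious or suspected reaction must be reported. The baby is neither randomised nor dosed, so the definitions in 9.2 do not plainly cover it, and the data items capture only chosen kinds of morbidity.

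Two things are at stake. First, the neonatal half of endpoint 12 could be reported as reassuring when unlisted harms were never asked about. Second, sites in five countries (Denmark, UK, Italy, Ireland, Canada) would have to infer for themselves whether an event in a newborn falls under the 24-hour reporting rule, so ascertainment could differ between sites.

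**Working it through.** The protocol gives no figure to reproduce here. The check is to follow example events through the text.

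1. **Is the baby a subject under 9.2?** Both definitions depend on administration or dosing of the subject. No section states that the fetus or neonate counts as one. The catch-all in 9.2.1 and the enquiry in 7.1 use the same defined term, so they inherit its scope.
2. **Are the neonatal items open-ended?** The lists in 4.3, 7.1 and 8.2 name bleeding or thrombosis, infection, congenital abnormality and days of care or stay, plus birth details. None has an entry for other events.
3. **Tracing examples:**

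| Event in the baby | AE under 9.2, read literally | Named data item | Other trace |
|---|---|---|---|
| Death after live birth | No | None | Possibly length of stay |
| Hypoglycaemia (listed in 5.3 as a drug effect) | No | None | Special-care or admission days, without cause |
| Marrow depression (listed in 5.3) | No | None, unless seen as bleeding or infection | As above |
| Serious infection | No | Yes, endpoint 8 | SAE status also removed by the outcome exemption |
| Congenital abnormality | Named as a seriousness criterion | Yes, endpoint 8 | SAE status removed by the outcome exemption |

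4. **Contradiction inside 9.2.** Congenital abnormality is both a criterion for seriousness and part of a secondary outcome measure whose events are declared not to be SAEs. Both statements cannot be applied to the same case.
5. **What endpoint 12 adds.** Neonatal information already sits in endpoints 4 (gestational age), 5 (birth weight), 7 (Apgar), 8 (morbidity), 9 (days to discharge) and 11 (days in special care). The protocol lists no neonatal item specific to endpoint 12.
6. **Newborn eye and ear tests.** Section 5.3 removes this screen from the current version. Section 9.1 still says that all babies will be tested within 6 weeks. The one dedicated neonatal safety assessment is thus stated both ways.
7. **Illustrative scale.** Inputs: 328 pregnancies and the retrospective live-birth rates of 67% with HCQ and 57% without (section 10.2). Assumptions: equal arms and singletons.
   - Per arm: 328 / 2 = 164.
   - Exposed live births: 164 × 0.67 = 110.
   - Unexposed live births: 164 × 0.57 = 93. Total: 203.
   - Rule of three for zero events in 110: 3 / 110 = 2.7% as the upper 95% limit.

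   The limit means something only for event types that sites are told to record.

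**The case against.** The wording in 9.2 is standard regulatory text, and the congenital anomaly criterion can only concern offspring, so the child was not wholly shut out. The catch-all in 9.2.1 and the post-partum enquiry are not limited to the mother, and the side-effect table in 5.3 includes ototoxicity and retinal toxicity in the newborn. A site could read all this generously and report neonatal events. Section 8.2 also obtains consent for access to the child's notes if needed. The eCRF, the pharmacovigilance policy cited in 9.2 and the data management plan in section 17 are not shown and may fill the gap. Finally, section 5.3 gives reasons for limiting newborn assessments.

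Much of this stands, and it rules out some stronger readings. A reader might infer that neonatal harms cannot be reported at all, or that the case report form is a closed list. The documents support neither: they show only that the protocol defines no route and that its own lists are enumerated. A reader might also infer that endpoint 12 holds nothing on neonates beyond endpoint 8. That is wrong, because five other endpoints carry neonatal information. Nor does 5.3 say that fetal exposure equals maternal exposure, only that the data suggest it is similar. Neonatal arrhythmia is a poor example: the cardiac entry in the 5.3 table is cardiac failure, and 5.3 reports no increase in conduction disturbance and normal electrocardiograms in exposed children.

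The objection does not supply a sentence extending 9.2 to the baby. Access to notes creates neither a duty to record nor a clock. The reasons in 5.3 concern extra examinations and do not address event reporting.

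**Conclusion.** The point holds as a gap and an internal inconsistency in the protocol text. Adverse event definitions are not expressly extended to the live-born baby, unlisted neonatal harms including death have no defined recording or reporting route, and the outcome exemption in 9.2 conflicts with its own congenital anomaly criterion. Endpoint 12 is therefore only partly answerable for the neonate.

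No error rate or power figure attaches to this. The figures of about 110 exposed babies and 2.7% illustrate what complete collection could exclude. They assume 164 pregnancies per arm, one baby each (section 7.1 provides for twins and triplets) and live-birth rates from a retrospective cohort. The conclusion rests on a literal reading of the protocol. If the unseen forms or policy already cover the baby, the practical loss is smaller, but the protocol should still say so. Scope of events and reporting clocks are set in section 9.2, so this is not a matter to leave to the statistical analysis plan.

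**What to change.** 1. In 9.2, state that the AE, SAE and SUSAR definitions also apply to the live-born baby from birth to the post-partum contact, recorded under the mother's participant number with the same reporting clock.
2. Narrow the outcome exemption in 9.2 so that it does not cover serious neonatal events, congenital anomalies or suspected reactions in the neonate. Without this, the first change leaves the listed neonatal events outside the 24-hour rule.
3. Add to the post-partum child items in 7.1 (and to 4.3 and 8.2) an entry for any other neonatal adverse event, including neonatal death, and report it by arm under endpoint 12.
4. Reconcile sections 5.3 and 9.1 on newborn eye and ear testing.

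The cost is protocol wording and one eCRF field. Randomisation, dosing and visits are untouched, and consent for access to the child's notes is already provided for in 8.2. The downsides are somewhat more event reports, mainly from preterm babies, and incomplete ascertainment for babies born before the amendment (5.3 shows that some had been born by November 2022) unless their records are completed from the child's notes. That limitation should be stated when endpoint 12 is reported.

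### Section 9.2 takes SAE status away from every outcome event, which contradicts its own SAE definition and the narrower exemption in section 9.2.1

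*Protocol*

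**What the plan says.** Section 9.2 sets out the criteria that make an event serious. One of them is: "Consists of a congenital anomaly or birth defect". Directly after the criteria comes the exemption: "Fetal death as a result of maternal disease and other events that are primary or secondary outcome measures are not considered to be SAEs". Events covered by it "should be reported in the normal way, on the appropriate CRF".

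The secondary endpoints in section 4.1.2, repeated in the synopsis and in section 8.1.1, include:

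- endpoint 8: "Neonatal morbidity (bleeding or thrombotic complications, infections, congenital abnormalities"
- endpoint 10: "Thrombotic events in the mother during pregnancy and 6 weeks post-partum"

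The expedited rule, also in section 9.2, reads: "All SAEs, SARs and SUSARs (excepting those specified in this protocol as not requiring reporting) will be reported immediately", with 24 hours as the outer limit.

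Section 9.2.1 gives a different exemption. Its first paragraph releases symptoms put down to normal pregnancy. Its second releases aPL-related pregnancy complications, introduced by an open-ended 'such as': early and later miscarriage, birth before 34 weeks because of pre-eclampsia, eclampsia or fetal growth restriction (FGR), and stillbirth. It closes: "Any other adverse events will be reported".

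**The concern.** The protocol gives two instructions for the same events. Under 9.2 a birth defect is an SAE by definition and, a sentence later, not an SAE because it is a secondary outcome. Under 9.2.1 it is outside the named exemptions and is to be reported.

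What is at stake is status and speed, since the data are captured either way. The eCRF is completed at trial visits (section 17). Neonatal morbidity is collected at the post-partum visit, up to 6 weeks after delivery, or at the third-trimester visit after a preterm delivery (sections 4.3 and 7.1). Details of a maternal stroke, myocardial infarction or other arterial thrombosis are obtained retrospectively from the treating centre (section 8.2). A site that relies on the CRF alone could therefore replace a 24-hour clock with one of weeks. The 7-day and 15-day SUSAR deadlines in section 9.2 run only from the time the sponsor becomes aware.

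**Working it through.** No figure in the plan bears on this point, so the check is textual: each class of event is taken through the three rules.

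| Event | SAE criteria in 9.2 | Exemption in 9.2 | Section 9.2.1 |
|---|---|---|---|
| Congenital anomaly | Always serious | Not an SAE (endpoint 8) | Not named, so reported |
| Neonatal bleeding, thrombosis or infection that meets a seriousness criterion | Serious | Not an SAE (endpoint 8) | Not named, so reported |
| Maternal thrombosis, pregnancy to 6 weeks post-partum, that meets a seriousness criterion | Serious | Not an SAE (endpoint 10) | Not named, so reported |
| Maternal thrombosis before pregnancy that meets a seriousness criterion | Serious | Not exempt: not a listed endpoint | Not named, so reported |
| Miscarriage; birth before 34 weeks from pre-eclampsia or eclampsia | May be serious | Not an SAE (primary endpoint) | Exempt |
| Birth before 34 weeks from placental insufficiency shown by features other than FGR | May be serious | Not an SAE (primary endpoint in the synopsis and 8.1.1) | Not named; only FGR is |

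Four things follow.

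1. In the first three rows the two exemptions give opposite answers. In the first row 9.2 also contradicts itself.
2. Section 9.2.1 does not settle the conflict. It says that other events are reported, but not that they are SAEs, and it gives no deadline. Its list is also open, so a site could argue that maternal thrombosis belongs on it.
3. The exemption in 9.2 names SAEs only, whereas the 24-hour rule names SAEs, SARs and SUSARs and then excludes whatever the protocol releases from reporting. Whether a suspected serious reaction that is also an outcome falls inside or outside that exclusion cannot be determined from the text.
4. The two exemptions agree on the complications that the trial expects to see, apart from the FGR wording in the last row.

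**The case against.** The strongest reply is that 9.2.1 is the operative list. The 24-hour rule excludes events that the protocol specifies as not needing to be reported, and this echoes the heading of 9.2.1. On that reading a birth defect stays reportable. This is a fair construction. It is why the point is a contradiction to be resolved and not proof that every outcome event escapes SAE reporting. It does not remove the sentence in 9.2, which a site may equally follow.

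A second reply concerns maternal thrombosis. It is a defining feature of antiphospholipid syndrome, and handling disease-related efficacy events as endpoints instead of SAEs is a legitimate choice. That stands. The protocol should say so explicitly if it is intended. The exemption could in any case cover only pregnancy and the 6 weeks after delivery.

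Some stronger readings are tempting but unsupported:

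- Endpoint 12, "Safety and tolerability of hydroxychloroquine in the mother and in the neonate", might seem to exempt all safety data. It is a domain and not an event, and that reading would empty 9.2 of content.
- A reader might conclude that SUSAR assessment is certainly lost. The exempting sentence names only SAEs, so the status is unclear and the loss is not established.
- A reader might infer that the Data Monitoring Committee is deprived of timely information. The 24-hour route runs to the trials office and the chief investigator, and the protocol nowhere links it to that committee.
- The SmPC pregnancy contraindication cited in section 5.3 might be taken as a sign of known fetal harm. The same section reports guideline support for use in pregnancy and no evidence of more malformations.

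**Conclusion.** The concern holds as an internal contradiction in the safety reporting rules. It should be corrected, because it concerns participant safety and the remedy is cheap. It affects two of the twelve secondary endpoints: all of endpoint 8 where the event is serious, and endpoint 10 within its stated time window. The case is clearest for congenital anomaly, which 9.2 both includes and excludes, then for serious neonatal events. Maternal thrombosis needs a stated rule more than it needs a particular one.

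The consequence is conditional. A site that follows 9.2 would have the event on the CRF but could bypass the 24-hour SAE route. Nothing in the documents shows how many sites read it that way. A reader might want to put a number on the anomalies affected. That would require an assumed anomaly rate, which the protocol does not give, and the further assumption that every site follows 9.2 over 9.2.1. The conclusion depends on neither. Capture of endpoint data is not in question.

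**What to change.** Amend section 9.2 as follows.

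- Replace the general exemption for outcome events with a closed list of the aPL-related pregnancy complications named in the second paragraph of 9.2.1. Do not point to 9.2.1 as a whole. That would bring in its paragraph on ordinary pregnancy symptoms, so that such a symptom might lose SAE status even if it led to hospital admission, as well as its open 'such as' wording.
- Align the list with the primary endpoint. Section 9.2.1 refers to FGR, while the synopsis and section 8.1.1 refer to features of placental insufficiency. Section 4.1.1 words the endpoint differently again, so the sponsor must first confirm which definition applies.
- State that congenital anomalies and serious neonatal bleeding, thrombosis or infection are both outcome data and SAEs.
- State that any suspected serious reaction is reported whether or not it is also an endpoint.
- State which route applies to maternal thrombosis in pregnancy and the 6 weeks post-partum.
- Make 9.2.1 carry the same closed list.

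Then send a memo to sites and check outcome CRFs already entered against SAE records once, to find events that took only the CRF route.

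The cost is a short amendment, the memo, one reconciliation and slightly more SAE forms. Treatment, sample size and efficacy analysis are unchanged.
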